4.1.1 Investigational Product

An investigational product, also known as investigational medicinal product in some regions, is defined as follows:

A pharmaceutical form of an active substance or placebo being tested or used as a reference in a clinical study, including products already with a marketing authorization but used or assembled (formulated or packaged) in a way different from the authorized form, or used for an unauthorized indication, or when used to gain further information about the authorized form.

The investigational product should be stored in a secure area according to local regulations. It is the responsibility of the investigator to ensure that investigational product is only dispensed to study subjects. The investigational product must be dispensed only from official study sites by authorized personnel according to local regulations.

In this protocol, investigational product(s) is/are: lirilumab, nivolumab, ipilimumab, and placebo.

4.1.2 Noninvestigational Product

Other medications used as support or escape medication for preventative, diagnostic, or therapeutic reasons, as components of the standard of care for a given diagnosis, may be considered as noninvestigational products.

In this protocol, noninvestigational product(s) is/are medications used to treat adverse events.

4.1.3 Handling and Dispensing

The product storage manager should ensure that the study drug is stored in accordance with the environmental conditions (temperature, light, and humidity) as determined by BMS. If concerns regarding the quality or appearance of the study drug arise, do not dispense the study drug and contact BMS immediately.

4.1.4 Preparation of Study Drug(s)

The study drugs will be administered by IV infusion. Details with regard to IV admixing, infusion rates, and stability will be provided separately in study site training materials and the Dosing Procedure Manual.

4.2 Method of Assigning Subject Identification

CA223001 is an open-label study with the exception of the SCCHN Randomized Cohorts (Part 3), which is site- and subject-blind. Subjects will undergo screening evaluations to determine eligibility within 28 days prior to dosing for the Dose Escalation and Cohort Expansion (Part 1) and the SCCHN Cohort Expansion (Part 2) and 35 days for all other study parts. Enrolled subjects will be assigned a subject number, [REDACTED] increasing sequentially with each additional enrolled subject. The subject number will be assigned by the Sponsor via IVRS once the subject signs the informed consent form. Each subject will then be identified by a distinct patient identification number (PID) which is composed of the study site number and the subject number. For example, the first subject screened (ie, enrolled) at study site number 1, will have a

PID [REDACTED]. The investigator or designee will register the subject following the enrollment procedures established by BMS. The following information is required for registration:

- Date of birth
- Gender
- Diagnosis
- Tumor Type
- Date of Informed Consent
- Planned date of 1st dose

Enrolled subjects meeting all eligibility criteria will be assigned to a dose cohort. Specific instructions regarding enrollment and dose cohort assignment will be provided to the study sites in their training materials.

The SCCHN Randomized Cohorts (Part 3)

The investigator or designee will register the subject for enrollment by following the enrollment procedures established by BMS for the SCCHN Randomized Cohorts (Part 3). Once enrolled in IVRS, enrolled subjects who have met all eligibility criteria and have been assigned to the SCCHN Randomized Cohorts (Part 3) will be ready to be randomized through the IVRS in a 2:1 ratio of Arm A to Arm B:

- Arm A: flat dose of lirilumab 240 mg Q4W (Days 1 and 29) and flat dose of nivolumab 240 mg Q2W (Days 1, 15, 29, and 43) until PD
- Arm B: placebo for lirilumab Q4W (Days 1 and 29) and flat dose of nivolumab 240 mg monotherapy Q2W (Days 1, 15, 29, and 43) until PD

The following information is required for subject randomization:

- Subject number
- Date of birth
- Prior cetuximab treatment (yes/no)
- PD-L1 status

The stratification factor includes:

- PD-L1 \geq 50% expression (yes/no)
- Prior cetuximab treatment (yes/no)

The first dose of study drug is to be administered within 3 days following randomization.

Specific instructions for using IVRS will be provided to the study sites in a separate document.

4.3 Selection and Timing of Dose for Each Subject

Each subject will be assigned to a specific Dose Level as listed in [Table 3.1.1.1-1](#) in sequential order during dose escalation. Subjects in cohort expansion will be treated at the MTD, the MAD, or at an alternate dose, if recommended by the investigators and the Sponsor.

Subjects in the SCCHN Randomized Cohorts (Part 3) will be treated with a flat dose of nivolumab 240 mg Q2W in combination with a flat dose of lirilumab 240 mg Q4W or placebo for lirilumab Q4W.

Subjects in the Signal Detection in SCCHN with Lirilumab, Nivolumab, and Ipilimumab Combination (Part 5) will be treated with a triplet combination of lirilumab 3 mg/kg Q4W, nivolumab 3 mg/kg Q2W, and ipilimumab 1 mg/kg Q6W. If conditions in [Section 3.1.5](#) are met, a lower dose or an alternate dose schedule should be examined.

4.4 Blinding/Unblinding

Applicable for the single-blinded SCCHN Randomized Cohorts (Part 3).

Blinding of treatment assignment is critical to the integrity of this clinical study. However, in the event of a medical emergency or pregnancy in an individual subject in which knowledge of the investigational product is critical to the subject's management, the blind for that subject may be broken by the investigator. The subject's safety takes priority over any other considerations in determining if a treatment assignment should be unblinded.

Before breaking the blind of an individual subject's treatment, the investigator should determine that the unblinded information is necessary, ie, that it will alter the subject's immediate management. In many cases, particularly when the emergency is clearly not related to the investigational product, the problem may be properly managed by assuming that the subject is receiving active product. It is highly desirable that the decision to unblind treatment assignment be discussed with the Medical Monitor, but the investigator always has ultimate authority for the decision to unblind. The Principal Investigator should only call in for emergency unblinding AFTER the decision to discontinue the subject has been made.

For this study, the method of unblinding for emergency purposes is the Interactive Response Technology (IRT).

In cases of accidental unblinding, contact the Medical Monitor and ensure every attempt is made to preserve the blind.

Any request to unblind a subject for non-emergency purposes should be discussed with the Medical Monitor.

In case of an emergency, the investigator(s) has unrestricted access to randomization information via the IRT and is capable of breaking the blind through the IRT system without prior approval from the Sponsor. Following the unblinding, the investigator shall notify the Medical Monitor and/or study director.

For information on how to unblind for emergency, please consult the IRT manual.

The subjects, investigator, and site staff will be blinded to the study drug administered (lirilumab in combination with nivolumab or nivolumab monotherapy). For all subjects in the SCCHN Randomized Cohorts (Part 3), and the Signal Detection in SCCHN with Lirilumab, Nivolumab, and Ipilimumab Combination (Part 5), each investigative site must assign an unblinded

pharmacist/designee and an unblinded site monitor will be assigned by sponsor to provide oversight of drug supply and other unblinded study documentation.

4.5 Treatment Compliance

Study drug will be administered in the clinical facility. The investigator or their designated study personnel will maintain a log (Drug Accountability Log) of all study drugs received, dispensed and destroyed. The investigator and the study personnel will ensure that each subject receives the calculated dose of the study drug based on body weight.

Drug supplies will be inventoried and accounted for throughout the study. The Drug Accountability Log will be reviewed by the study monitor during study site visits and at the completion of the study. Any discrepancy should be brought to the attention of the Sponsor. For the SCCHN Randomized Cohorts (Part 3), treatment compliance will be monitored by drug accountability as well as the subject's medical record and CRF.

4.6 Destruction and Return of Study Drug

4.6.1 Destruction of Study Drug

If study drugs (those supplied by BMS or sourced by the investigator) are to be destroyed on site, it is the investigator's responsibility to ensure that arrangements have been made for the disposal, procedures for proper disposal have been established according to applicable regulations, guidelines and institutional procedures, and appropriate records of the disposal have been documented. The unused study drugs can only be destroyed after being inspected and reconciled by the responsible BMS Study Monitor.

4.6.2 Return of Study Drug

If study drug will not be destroyed upon completion or termination of the study, all unused and/or partially used study drug that was supplied by BMS must be returned to BMS. The return of study drug will be arranged by the responsible BMS Study Monitor.

It is the investigator's responsibility to arrange for disposal of all empty containers, provided that procedures for proper disposal have been established according to applicable federal, state, local, and institutional guidelines and procedures, and provided that appropriate records of disposal are kept.

4.7 Retained Samples for Bioavailability / Bioequivalence

Not applicable

4.8 Dose Limiting Toxicities

This section only applies to the Dose Escalation and Cohort Expansion (Part 1) and the SCCHN Cohort Expansion (Part 2), which have both completed enrollment and therefore this section and its subsections are not applicable starting with Amendment 13 and all subsequent amendments or revised protocols.

4.8.1 Definition

DLT will be determined based on the incidence, intensity, and duration of AEs as defined below that are related to study drug and that occur within 56 days (8 weeks, through the completion of Cycle 1) of initiation of study drug in the Dose Escalation and Cohort Expansion (Part 1; completed). The severity of AEs will be graded according to the NCI CTCAE v4.03. Hepatic, non-hematologic, and hematologic DLT will be defined separately as outlined below.

4.8.2 Definition of Hepatic DLT

Any of the following events will be considered a hepatic DLT except for subjects with HCC:

- ALT or AST $> 8 \times$ ULN, regardless of duration
- ALT or AST $> 5 \times$ and $\leq 8 \times$ ULN, that fails to return to Grade 1 or less within 5 days despite medical intervention
- Grade 3 total bilirubin
- ALT or AST $> 3 \times$ ULN and concurrent total bilirubin $> 2 \times$ ULN

4.8.2.1 Definition of Hepatic DLT for Subjects with HCC

In August 2011, an advisory board panel was convened to discuss treatment of subjects with hepatitis B infection with or without HCC. The potential for hepatic flare with anti-viral therapy such as entecavir, lamivudine, or tenofovir was discussed. It was the consensus of the panel members that the risk for this toxicity was low in subjects with low viral DNA loads who were on anti-viral therapy for several months. In subjects with hepatitis C infection, transient Grade 4 transaminase levels can be observed. Protocol Section 4.8.2 describes the hepatic toxicity DLT parameters used for subjects without HCC for this protocol. Due to the potential for hepatic inflammation that could be greater due to viral infection the panel recommended that parameters be adjusted to permit a higher level of hepatic toxicity with AST or ALT $> 10 \times$ ULN for > 2 weeks, AST or ALT $> 15 \times$ ULN irrespective of duration, total bilirubin $> 8 \times$ ULN irrespective of duration for subjects with elevated bilirubin at study entry or $> 5 \times$ ULN for those with normal total bilirubin at study entry, concurrent AST or ALT $> 3 \times$ ULN and total bilirubin $> 5 \times$ ULN for subjects entering treatment with a normal bilirubin and up to $8 \times$ ULN for subjects with elevated bilirubin, or clinical deterioration manifested by drug-related hepatic decompensation not identified above.

Therefore, for subjects with HCC, hepatic DLT criteria will differ due to intrinsic involvement of the liver. In addition, for subjects with hepatitis B or hepatitis C, it is possible that virological breakthrough may occur, leading to temporary hepatic damage that is greater than the parameters detailed above. In these cases, subjects who regain virologic control may be allowed to resume study therapy after agreement between the PI and the Medical Monitor.

Any of the following events will be considered a hepatic DLT for subjects with HCC:

- ALT or AST $> 15 \times$ ULN, regardless of duration
- ALT or AST $> 10 \times$ ULN for greater than 2 weeks

- total bilirubin $> 8 \times$ ULN regardless of duration for subjects with elevated bilirubin at study entry or $> 5 \times$ ULN for subjects with normal bilirubin at study entry
- ALT or AST $> 3 \times$ ULN and concurrent total bilirubin $> 2 \times$ ULN

4.8.3 Definition of Non-hematologic DLT

Any of the following events will be considered a non-hematologic DLT:

- Grade 2 eye pain or reduction in visual acuity that requires systemic treatment
- Grade 2 eye pain or reduction in visual acuity that does not respond to topical therapy and that does not improve to Grade 1 within 2 weeks of initiation of topical therapy
- Grade 3 non-hepatic or non-hematologic toxicity, with the following exceptions:

The following Grade 3 non-hematologic events **will not** be considered DLTs:

- Grade 3 electrolyte abnormality that lasts less than 72 hours, is not clinically complicated, and resolves spontaneously or responds to conventional medical intervention
- Grade 3 increase in amylase or lipase that is not associated with clinical or radiographic evidence of pancreatitis
- Grade 3 nausea or vomiting that lasts less than 48 hours, and resolves to Grade 1 or less, either spontaneously or with conventional medical intervention
- Grade 3 fever that lasts less than 72 hours, and is not associated with hemodynamic compromise (including hypotension, or clinical or laboratory evidence of end organ perfusion impairment)
- Grade 3 endocrinopathy that is well controlled by hormone replacement
- Grade 3 tumor flare (defined as pain, irritation or rash that localizes to sites of known or suspected tumor)
- Grade 3 fatigue
- Grade 3 infusion reaction that returns to Grade 1 in less than 6 hours

4.8.4 Definition of Hematologic DLT

Any of the following events will be considered a Hematologic DLT:

- Grade 4 neutropenia that lasts longer than 5 days
- Grade 4 thrombocytopenia
- Grade 3 thrombocytopenia associated with clinically significant bleeding
- Grade 3 febrile neutropenia that lasts longer than 48 hours
- Grade 3 hemolysis

4.9 Guidelines for Dose Modification

Intra-subject dose escalation or reduction of lirilumab, nivolumab, and ipilimumab is not permitted in this study in order to allow better evaluation of extended safety and efficacy at individual Dose Levels and schedules.

4.9.1 Intra-subject Dose Escalation

No intra-subject dose escalation is allowed.

4.9.2 Dose Reductions

No dose reductions of lirilumab, nivolumab, and ipilimumab are permitted in this study.

4.9.3 Dose Delays Due To Toxicity

Subjects who experience a DLT must have therapy held. Subjects who are required to permanently discontinue study drug administration are listed in [Section 4.9.5](#). All other subjects will be permitted to resume study drug administration at the same doses for all study drugs following resolution of the AE to Grade 1 or less, or to baseline.

Study drug administration should be delayed for the following:

- Grade 2 non-skin, drug-related AE, with the exception of fatigue
- Grade 2 drug-related creatinine, AST, ALT, and/or total bilirubin abnormalities
- Grade 3 skin, drug-related AE
- Grade 3 drug-related laboratory abnormality, with the following exceptions:
 - Grade 3 lymphopenia or asymptomatic amylase or lipase does not require dose delay
 - Grade ≥ 3 AST, ALT, and total bilirubin will require dose discontinuation (see [Section 4.8](#))
- Any AE, laboratory abnormality, or intercurrent illness, which, in the judgment of the investigator, warrants delaying the dose of study drug

Subjects who require delay of nivolumab should be re-evaluated weekly or more frequently if clinically indicated and resume nivolumab dosing when retreatment criteria are met.

4.9.4 Criteria for Subsequent Dosing

Subsequent dosing may continue if subjects continue to meet laboratory criteria as listed in [Section 3.3.1](#). The investigator will determine if subsequent dosing is appropriate for subjects who have laboratory or clinical abnormalities that do not meet DLT (Section 4.8) or discontinuation criteria (Section 4.9.5). All related Grade 2 toxicities should be discussed with the BMS Medical Monitor prior to subsequent dosing.

Subjects may resume treatment with study drug when the drug-related AE(s) resolve to Grade ≤ 1 or baseline value, with the following exceptions:

- Subjects may resume treatment in the presence of Grade 2 fatigue.
- Subjects who have not experienced a Grade 3 drug-related skin AE may resume treatment in the presence of Grade 2 skin toxicity.
- For subjects with Grade 2 AST, ALT, and/or total bilirubin abnormalities, dosing may resume when laboratory values return to baseline and management with corticosteroids, if needed, is complete.
- Subjects with combined Grade 2 AST/ALT and total bilirubin values meeting discontinuation parameters (Section 4.8) should have treatment permanently discontinued.
- Drug-related pulmonary toxicity, diarrhea, or colitis must have resolved to baseline before treatment is resumed. Subjects with persistent Grade 1 pneumonitis after completion of a steroid taper over at least 1 month may be eligible for retreatment if discussed with and approved by the BMS Medical Monitor.

- Subjects with drug-related endocrinopathies adequately controlled with only physiologic hormone replacement may resume treatment after consultation with the BMS Medical Monitor. Adrenal insufficiency requires discontinuation regardless of control with hormone replacement.

4.9.5 Guidelines for Permanent Discontinuation

Subjects will be required to permanently discontinue all study drugs for the following AEs:

- 1) Any Grade 2 drug-related uveitis, eye pain, or blurred vision that does not respond to topical therapy and does not improve to Grade 1 severity within the retreatment period OR requires systemic treatment
 - 2) For subjects receiving lirilumab in combination with nivolumab or nivolumab monotherapy (the Dose Escalation and Cohort Expansion [Part 1; completed] and the SCCHN Cohort Expansion [Part 2; completed], the SCCHN Randomized Cohorts [Part 3],): Any Grade 3 non-skin, drug-related AE lasting > 7 days or recurs, with the following exceptions for laboratory abnormalities, drug-related uveitis, pneumonitis, bronchospasm, hypersensitivity reactions, infusion reactions, and endocrinopathies:
 - a) Grade 3 drug-related uveitis, pneumonitis, bronchospasm, hypersensitivity reaction, or infusion reaction of any duration requires discontinuation.
 - b) Grade 3 drug-related endocrinopathies, adequately controlled with only physiologic hormone replacement, do not require discontinuation. Adrenal insufficiency requires discontinuation regardless of control with hormone replacement.
 - c) Grade 3 drug-related laboratory abnormalities do not require treatment discontinuation except:
 - i) Grade 3 drug-related thrombocytopenia > 7 days or associated with bleeding
 - ii) Grade ≥ 3 drug-related AST, ALT, or total bilirubin*
 - iii) Concurrent AST or ALT > $3 \times$ ULN and total bilirubin > $2 \times$ ULN
- * In most cases of Grade 3 AST or ALT elevation, study drug(s) will be permanently discontinued. If the investigator determines a possible favorable benefit/risk ratio that warrants continuation of study drug(s), a discussion between the investigator and the BMS Medical Monitor/designee must occur.
- 3) For subjects receiving lirilumab in combination with nivolumab and ipilimumab (the Signal Detection in SCCHN with Lirilumab, Nivolumab, and Ipilimumab Combination [Part 5]): Any Grade 3 non-skin, drug-related AE lasting > 7 days, or recurs with the following exceptions for laboratory abnormalities, diarrhea, colitis, neurologic toxicity, drug-related uveitis, pneumonitis, bronchospasm, hypersensitivity reactions, infusion reactions, and endocrinopathies:
 - a) Grade 3 drug-related diarrhea, colitis, neurologic toxicity, uveitis, pneumonitis, bronchospasm, hypersensitivity reaction, or infusion reaction of any duration requires discontinuation.
 - b) Grade 3 drug-related endocrinopathies, adequately controlled with only physiologic hormone replacement, do not require discontinuation. Adrenal insufficiency requires discontinuation regardless of control with hormone replacement.

- c) Grade 3 drug-related laboratory abnormalities do not require treatment discontinuation except:
 - iv) Grade 3 drug-related thrombocytopenia > 7 days or associated with bleeding
 - v) Any drug-related liver function test abnormality that meets the following criteria:
 - (1) Grade ≥ 3 drug-related AST, ALT, or total bilirubin*
 - (2) Concurrent AST or ALT > $3 \times$ ULN and total bilirubin > $2 \times$ ULN

* In most cases of Grade 3 AST or ALT elevation, study drug(s) will be permanently discontinued. If the investigator determines a possible favorable benefit/risk ratio that warrants continuation of study drug(s), a discussion between the investigator and the BMS Medical Monitor/designee must occur.

- 4) Any Grade 4 drug-related AE or laboratory abnormality (including but not limited to creatinine, AST, ALT, or total bilirubin), except for the following events, which do not require discontinuation:
 - a) Isolated Grade 4 electrolyte imbalances/abnormalities that are not associated with clinical sequelae and are corrected with supplementation/appropriate management within 72 hours of their onset
 - b) Grade 4 neutropenia ≤ 7 days
 - c) Grade 4 lymphopenia or leukopenia or asymptomatic amylase or lipase
 - d) Grade 4 lymphopenia < 5 days in duration
 - e) Grade 4 drug-related endocrinopathy AEs, such as hyper- or hypothyroidism, or glucose intolerance, which resolve or are adequately controlled with physiologic hormone replacement (corticosteroids or thyroid hormones) or glucose-controlling agents, respectively, may not require discontinuation after discussion with and approval from the BMS Medical Monitor.
- 5) Any DLT as outlined in [Section 4.8](#) will require permanent discontinuation with the following exceptions:
 - a) Grade 3 diarrhea, nausea, vomiting, or abdominal pain that returns to Grade 1 or baseline within 3 days with medical intervention
 - b) Grade 3 ALT or AST that returns to Grade 1 or baseline within 7 days with medical intervention
 - c) Grade 3 pruritus or rash that returns to Grade 1 or baseline within 7 days or baseline with medical intervention
- 6) Any event that leads to delay in dosing lasting > 6 weeks from the previous dose requires discontinuation, with the following exceptions:
 - a) Dosing delays to allow for prolonged steroid tapers to manage drug-related AEs are allowed.
 - b) Dosing delays lasting > 6 weeks from the previous dose that occur for non-drug-related reasons may be allowed if approved by the BMS Medical Monitor.
 - c) Prior to re-initiating treatment in a subject with a dosing delay lasting > 6 weeks, the BMS Medical Monitor must be consulted. Tumor assessments should continue as per protocol even if dosing is delayed. Periodic study visits to assess safety and laboratory studies

should also continue Q6W or more frequently if clinically indicated during such dosing delays.

7) Any AE, laboratory abnormality, or intercurrent illness, which, in the judgment of the investigator, presents a substantial clinical risk to the subject with continued nivolumab dosing. The consideration to re-initiate study therapy under these exceptions will be made on a case by case basis after considering the overall benefit/risk profile and in consultation between the investigator and the study Sponsor.

In cases where the AE meets the criteria for permanent discontinuation from study therapy, but the investigator and the Sponsor believe that re-initiation of study therapy may be potentially beneficial and justified, details will be submitted in advance to the FDA or other relevant health authorities for review, prior to re-initiation of study therapy.

The assessment for discontinuation of nivolumab should be made separately from the assessment made for discontinuation of lirilumab and/or ipilimumab. Although there is overlap among the discontinuation criteria, if discontinuation criteria are met for lirilumab and/or ipilimumab but not for nivolumab, treatment with nivolumab may continue if lirilumab and/or ipilimumab is discontinued.

If a subject in any of the study drug combination cohorts meets criteria for discontinuation and investigator is unable to determine whether the event is related to a single study drug, the subject should discontinue all study drugs and be taken off the treatment phase of the study.

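### Protocol 4.9.5 item 4e can be read to let controlled Grade 4 adrenal insufficiency continue with Medical Monitor approval, while 4.9.4 and items 2b and 3b require it to stop

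*Protocol*

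**What the plan says.** Four places in the protocol bear on a drug-related endocrine event.

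- **Section 4.9.4 (resuming dosing).** The general rule is "Subjects with drug-related endocrinopathies adequately controlled with only physiologic hormone replacement may resume treatment after consultation with the BMS Medical Monitor". The next sentence takes one event out of it: "Adrenal insufficiency requires discontinuation regardless of control with hormone replacement". Neither sentence carries a grade.
- **Section 4.9.5 item 2b (Parts 1, 2 and 3)** and **item 3b (Part 5).** Each says "Grade 3 drug-related endocrinopathies, adequately controlled with only physiologic hormone replacement, do not require discontinuation", and each then repeats the adrenal sentence of 4.9.4.
- **Section 4.9.5 item 4 (no regimen named).** Grade 4 drug-related events end treatment, "except for the following events, which do not require discontinuation". Exception 4e covers "Grade 4 drug-related endocrinopathy AEs, such as hyper- or hypothyroidism, or glucose intolerance". To qualify, an event must be among those "which resolve or are adequately controlled with physiologic hormone replacement (corticosteroids or thyroid hormones) or glucose-controlling agents". The clause then states that such events "may not require discontinuation after discussion with and approval from the BMS Medical Monitor". The adrenal sentence does not appear here.

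**The concern.** The same adrenal sentence follows both Grade 3 endocrinopathy clauses and stands without a grade in 4.9.4, but it is absent from the Grade 4 clause. A reader who goes to Section 4.9.5 with a Grade 4 adrenal event controlled on replacement steroids can take that omission as deliberate and conclude that treatment may continue if the Medical Monitor agrees. A reader who starts from 4.9.4 concludes that it must stop.

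Three things are at stake.

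- **Subjects still on treatment.** Revised Protocol 12 closes enrolment but lets subjects with clinical benefit stay on study drug until they meet the protocol's discontinuation criteria. Those criteria are what conflict.
- **The route to restarting.** Near its end, Section 4.9.5 requires details to go to the FDA or other health authorities in advance if treatment is to be restarted after an event that met the permanent discontinuation criteria. Under item 4e, Medical Monitor approval is enough. The reading chosen decides whether the regulatory step applies.
- **A foreseeable event.** Section 1.1.4.1 lists adrenal insufficiency and hypophysitis among drug-related serious events in the nivolumab plus ipilimumab cohorts of another study. One of those cohorts (Arm Q) used the same doses and schedule of those two drugs as Part 5. Section 1.4.13.3 reports a related serious event of hypopituitarism with lirilumab plus ipilimumab.

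**Working it through.** No arithmetic applies. The check sets the rules side by side for one case: drug-related adrenal insufficiency, adequately controlled on corticosteroid replacement.

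| Rule | Grade covered | Action for this case |
|---|---|---|
| 4.9.4 | none stated | must discontinue |
| 4.9.5 item 2b (Parts 1, 2, 3) | sits in the Grade 3 item | must discontinue |
| 4.9.5 item 3b (Part 5) | sits in the Grade 3 item | must discontinue |
| 4.9.5 item 4e (no regimen named) | 4 | if 4e applies, may continue after Medical Monitor approval |

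**Step 1: does 4e reach adrenal insufficiency?** It does not name it; the examples are thyroid disorders and glucose intolerance. Two features let it be read that way. The examples are introduced as illustrations, so the list is open. The accepted control includes corticosteroids as physiologic hormone replacement, and elsewhere the protocol links replacement steroids to the adrenal gland: exclusion criterion 2l in Section 3.3.2 and Sections 3.4.2 and 3.4.3 all refer to adrenal replacement steroid doses.

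**Step 2: if it does, what follows?** Within Section 4.9.5, Grade 3 gives a mandatory stop and Grade 4 gives conditional permission to continue. Item 4e also conflicts directly with 4.9.4, whose sentence has no grade limit.

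**Step 3: is the conflict settled elsewhere?** No order of precedence is stated. Section 4.9.4 leaves subsequent dosing to the investigator for abnormalities that do not meet the discontinuation criteria of 4.9.5, so it refers back to the section that contains 4e. Section 3.5 also sends protocol-defined discontinuation to 4.9.5.

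**Step 4: how far does the reversal by grade go?** Only to adrenal insufficiency. For any other controlled endocrinopathy, item 4e is the stricter clause within 4.9.5, because it asks for approval where 2b and 3b do not.

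**Step 5: what reaches the analysis?** SAP Section 4.1 counts adverse events leading to discontinuation among the safety measures, and SAP Section 7.6.4 summarises them. SAP Section 7.1 puts all Part 3 and Part 5 results in listings only, and SAP Section 7.6 builds the safety tables from Parts 1 and 2 combined. No summary count for Part 3 or Part 5 is planned that could shift.

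**The case against.** The strongest reply is that the protocol already answers the question. The adrenal sentence is specific to one event, carries no grade of its own, and appears three times. Item 4e is a general clause that never names the event and pairs its examples with their treatments. A specific, repeated prohibition can reasonably be read as governing a general permission. Section 4.9.4 can also be read as a second condition: 4e only lifts automatic permanent discontinuation, and a subject excused by it would still fail 4.9.4 when dosing is to resume. This reading is available and may be what the authors meant. It does not settle the matter, because the text gives no precedence and 4.9.4 itself defers to 4.9.5.

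Other parts of the reply stand and limit the point.

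- A reader might infer that the two rules order opposite actions in every such event. They do not: one is mandatory, the other is permission that depends on approval.
- A reader might infer that two sites could freely act in opposite ways. Item 4e cannot be used without the sponsor's Medical Monitor, which limits divergence, and item 7 still requires a stop where the investigator sees substantial clinical risk. The Monitor is, however, given no rule to apply.
- A reader might infer that reported discontinuation counts depend on which line is followed. With Parts 3 and 5 in listings only, that largely falls away, and nothing here bears on the response rate endpoint.
- Exposure is limited. Parts 1 and 2 are complete and Parts 3 and 5 are closed to enrolment. Neither the 322-subject safety summary in Section 1 nor the Part 5 lead-in summary in Section 1.5 mentions a Grade 4 adrenal event, though neither is a full listing.
- The endocrinopathy algorithm (Appendix 1, Figure 5) could not be read in the text available, so whether it addresses this case is unchecked.

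**Conclusion.** The inconsistency is real, in a limited form. Three statements require discontinuation for adrenal insufficiency whatever the control. A fourth, for Grade 4 endocrinopathies, can be read to allow conditional continuation and lacks the adrenal sentence. The conclusion rests on reading 4e's open list and its mention of corticosteroids as reaching adrenal insufficiency, and on the absence of any stated precedence between 4.9.4 and 4.9.5. It does not rest on 4e naming the event, because it does not.

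The size cannot be put in numbers. The documents give no frequency for Grade 4 adrenal events, and there may be few or none among the subjects who remain. What matters is subject safety and uniform handling of a Grade 4 event while anyone is still being dosed. The documents do not support a claim that a worse grade is treated more leniently in general, or that planned summary tables would change materially. This review takes no position on which rule is clinically right.

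**What to change.** Reconcile Section 4.9.5 item 4e with Section 4.9.4 and items 2b and 3b, so that one stated rule covers adrenal insufficiency at every grade and for every regimen. The clinical team must choose that rule. When the clause is drafted, check Appendix 1, Figure 5 against it.

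The cost is one clause in Section 4.9.5, by administrative letter or in the next amendment. It changes no sample size, endpoint or planned analysis.
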